## Procedure

This study implements a quantitative data collection method. Participants will be invited to participate in the study through email. The researcher will send the invitation email to year three nursing students with inclusion criteria being those who have completed the subject “Clinical reasoning and decision making in action part 1”.

Participants will be invited to participate in the questionnaires on two-time points along the semester: before the teaching activity as the baseline and immediately after the usual teaching activity or intervention.

Before administering the questionnaire, an explanation of the research will be given to the students regarding the purpose of the study. They have the right to withdraw from the study at any time without any consequences. The data collected by this research will be treated as

entirely confidential. Participation is completely voluntary, and participants must agree to provide informed consent to participate in this research. Upon their agreement to participate, they will conduct three assessments throughout their academic year. The details can refer to in the Consort flow diagram as below.

## Instrumentation

The study aims to assess students' situation awareness, communication skills and self-confidence in learning. Two validated instruments are used to measure the dependent variables.

The first and second dependent variables, student's situation awareness and communication skills, will be tested using the revised "NOn-TECHnical skills (NOTECHS)" scale (Sevidalis et al., 2008). The scale is a widely accepted instrument to measure health care workers non-technical skills. The scale consists of 22 items with five subscales, including communication and interaction, situation awareness and vigilance, cooperation and team skills, leadership and managerial skills and decision making. The correlation coefficients for the five subscales reported range from ( $\alpha$  .77 - .87), demonstrated promising evidence of internal consistency of all subscales.

The third dependent variable, student's self-confidence in learning, will be tested using the "Student satisfaction and self-confidence in Learning" inventory (National League for Nursing, 2005). A total of 13 items assess the attitudes toward satisfaction with instruction and self-confidence in learning in simulation. A "satisfaction with instruction" subscale contains five items measuring satisfaction with teaching methods, diversity of learning materials, facilitation, motivation, and overall suitability of simulation. A "self-confidence with learning" subscale contains eight items measuring self-confidence in content mastery, content necessity, skills development, available resources, and knowledge of how to obtain help to solve clinical problems in simulation. Participants indicate their personal feelings about a statement that describes their attitudes or beliefs for each item. Response options include 1) strongly disagree, 2) disagree, 3) undecided, 4) agree, and 5) strongly agree according to Likert-style scale. Cronbach's alpha was reported as 0.94 for the satisfaction subscale and 0.87 for the self-

confidence subscale (Jeffries and Rizzolo, 2006). Scores are calculated by summing responses; higher scores indicate more satisfaction and more self-confidence, respectively.

Apart from the instruments, students' demographic data will be collected, including the prior experience in VR use to see whether previous VR experiences will affect the result.

Qualitative questions will be asked during the debriefing sessions after the VR experience to supplement the quantitative results. In addition, the debriefing guiding questions will be provided to the facilitators. Besides, the debriefing session will be video recorded for data analysis purposes.

### Data Analysis

The quantitative data will be analyzed using IBM SPSS for Windows version 26. Frequency and/or mean will be used to describe the demographic data. Descriptive data such as mean and median will describe the prevalence of attitudes and self-confidence, level of situation awareness and communication skills. Mann-Whitney U test will be used to examine the changes in mean scores of variables (attitudes and self-confidence, level of situation awareness and communication skills) between the control and experimental groups. A content analysis of the qualitative data will be conducted for the data collected from the debriefing session.

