## **Methodology**

### Study design

The study employs a quasi-experimental, pretest-posttest non-equivalent waitlist control group design. It is unethical to forbid a group of students from receiving a potential beneficial educational intervention for their learning purposes. In contrast, a waitlist design is appropriate to address the concern. The control group will not receive the intervention until after data has been collected. A pretest-posttest method will be used because of possible differences between the two groups.

Two intact groups, which cannot be randomly assigned, serve as the control and intervention groups. The intervention group will be having the VR training, whereas the control group will not until the study is completed.

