## Participants

Students studying Bachelor of Science in Nursing who have completed the subject “Clinical reasoning and decision making in action part 1” are eligible to participate in the study (n=200). The researcher accepts a margin of error at 5%, confidence interval at 95% and standard deviation of 0.5. By using the Z-score formula (*Necessary Sample Size = (Z-score)2 \* StdDev\*(1-StdDev) / (margin of error)2*), the sample size should be  $N = 132$ . To avoid dropout and attrition from the participants, the researcher will recruit 150 samples to participate in the study.

Convenience sampling will be adopted to recruit subjects. Participants will be assigned to two study groups, the control and the experimental group. The Control group will have usual teaching activities (simulation), whereas the participants of the intervention group, will have VR sessions.

[figure not shown]

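### Prior VR experience is collected to see whether it affects the result, but no planned analysis uses it, and no group difference with a confidence interval is planned for two non-randomised intact groups

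*Combined protocol and SAP*

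**What the plan says.** Under Instrumentation, demographic data are collected, "including the prior experience in VR use to see whether previous VR experiences will affect the result". The Data Analysis section gives them one use: "Frequency and/or mean will be used to describe the demographic data". For the outcomes, "Descriptive data such as mean and median will describe the prevalence of attitudes and self-confidence", and likewise situation awareness and communication skills. The only inferential step is "Mann-Whitney U test will be used to examine the changes in mean scores of variables", comparing the control and experimental groups. The section ends with a content analysis of the debriefing data.

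On the design, the Study design section says: "Two intact groups, which cannot be randomly assigned, serve as the control and intervention groups". It adds: "A pretest-posttest method will be used because of possible differences between the two groups". The Participants section describes the contrast: "The Control group will have usual teaching activities (simulation), whereas the participants of the intervention group, will have VR sessions". Sampling is by convenience.

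**The concern.** A frequency table of prior VR experience cannot show whether it affected the result. That needs an analysis relating prior VR to the outcome (a regression, a stratified test or an interaction), and none is planned. The study report could not answer a question the protocol itself raises, unless a method and a coding of prior VR were chosen after the data were seen.

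The design makes this more than a reporting matter. Without randomisation, the groups may differ in prior VR. A pretest deals with differences that shift both scores equally. It does not deal with a characteristic that changes how much a student gains. If prior VR is such a characteristic and is unevenly spread, part of its effect would be read as an effect of the VR training.

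Prior VR might also act only in the VR arm, since controls have simulation. It would then modify the effect, and a single comparison averages over it. Finally, a Mann-Whitney test alone yields a p-value, so readers would not learn how large the group difference is or how precisely it is known.

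**Working it through.** **Sample size used for illustration.** The protocol's N = 132 comes from a precision formula for one proportion: 1.96² × 0.5 × 0.5 / 0.05² = 384.16. With a finite-population correction for the 200 eligible students, which is not printed, 384.16 / (1 + 383.16/200) = 131.75, rounded up to 132. This figure is not disputed here. It is not a two-group calculation, so it says nothing about the precision of the group difference. Half of it, 66 per group, is used below; the allocation ratio is not stated.

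**Assumed inputs (none are in the documents).** Scores have SD 1 and pre/post correlation r = 0.5, so the change score has SD √(2(1 − 0.5)) = 1. There is no true VR effect, and prior VR acts equally in both arms. The share with prior VR differs by 10, 20 or 30 points, and its effect is 0.2, 0.5 or 0.8 SD.

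**Bias of the planned test on change scores.** Bias = (difference in shares) × (effect on the gain). The standard error, with Mann-Whitney efficiency 0.955, is √(2 / (66 × 0.955)) = 0.178. The rejection rate is 1 − Φ(1.96 − bias/0.178) + Φ(−1.96 − bias/0.178). The simulations used 10,000 runs per case.

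| Effect on post-test only | Bias (SD) | Formula | Simulation |
|---|---|---|---|
| 10 points, 0.2 SD | 0.1 × 0.2 = 0.02 | 5.1% | 5.3% |
| 20 points, 0.5 SD | 0.2 × 0.5 = 0.10 | 8.7% | 8.4% |
| 30 points, 0.8 SD | 0.3 × 0.8 = 0.24 | 27.1% | 24.6% |

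The formula overshoots in the last row because prior VR also adds variance within each arm.

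**If prior VR also affects the pre-test:**
- Half the effect already present: the bias falls to 0.2 × 0.25 = 0.05 SD (6.0%) and 0.3 × 0.4 = 0.12 SD (10.0%) in the last two cases.
- Equal effect at both times: the bias is 0 (simulated 4.8% and 5.2%).

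**Regressions that include prior VR.** In all these cases, two models stayed close to 5%: post-test on group, baseline and prior VR; and change on group and prior VR. This holds only when the groups have no separate baseline gap. With a 0.3 SD gap and r = 0.5:
- Stable gap: the baseline-adjusted model is biased by (1 − 0.5) × 0.3 = 0.15 SD and rejects 15.7%. The change-score regression rejects 4.8% and the Mann-Whitney test on change 5.1%.
- Groups regressing to a common mean: the change score is biased by 0.5 × 0.3 − 0.3 = −0.15 SD. The change-score regression rejects 13.5% and the Mann-Whitney test on change 13.3%, against 4.8% for the baseline-adjusted model.

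**Unreported precision.** The 95% half-width for a mean difference in change is 1.96 × √(2/66) = 0.34 SD. For the baseline-adjusted model it is about 0.31 SD at r = 0.5.

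**Effect only in the VR arm.** If prior VR adds 0.5 SD there and half the arm has it, the single averaged difference is 0.5 × 0.5 = 0.25 SD. With 40% prior VR in each arm, the interaction's 95% half-width is about 0.60 SD at r = 0.5.

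**The case against.** The strongest defence is that the plan already has a remedy. It gives possible group differences as the reason for a pretest-posttest method and then tests changes, so each student's own baseline is accounted for. That stands. A reader might infer that the test is wholly unadjusted, or that it compares post-test scores only, in which case even an equal effect of prior VR at both times would bias it. The wording does not spell out individual change scores, but they are the natural reading, and the post-test reading should carry no weight. What remains is that no other covariate is used.

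A second objection is that the obvious replacement, a baseline-adjusted regression as the primary analysis, is not clearly better. That also stands. With a stable 0.3 SD baseline gap plus prior-VR imbalance (20 points, 0.5 SD), it rejected about 16% of the time, against 8% to 9% for the planned test and about 5% for the change-score regression. The documents do not say how baseline differences would evolve, so they do not settle which model should lead. Nor is power an argument for using prior VR. At a true effect of 0.4 SD and r = 0.5, the baseline-adjusted model has 73.5% power, against 61.2% for the change-score regression and 60.3% for Mann-Whitney on change. The gain comes from the baseline score.

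Third, a regression without an interaction term averages over effect modification just as the rank test does. That is correct; only the interaction addresses it, and imprecisely.

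None of this supplies the missing analysis of prior VR or the missing interval.

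**Conclusion.** The concern holds in this form: prior VR experience has a stated analytic purpose and no analysis beyond description; the single between-group test uses no covariate other than the student's own baseline; and no group difference with an interval is planned. This rests on the text alone and needs no assumption.

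The size of any bias is conditional: negligible at a 0.2 SD effect (5.3% to 6.4% false positives for imbalances of 10 to 30 points), about 8% in the middle case, and about 25% only in the extreme corner. A reader might infer that the study's result will be confounded by prior VR. The documents do not support that, because they give neither its distribution nor its effect, and an equal shift at both time points cancels on change scores. The point is a cheap improvement, not a flaw that invalidates the comparison.

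**What to change.** In Data Analysis, for every outcome named there:

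1. State that the Mann-Whitney test uses individual change scores, and report its Hodges-Lehmann shift with a 95% CI.
2. Add two prespecified regressions with heteroscedasticity-robust standard errors: change score on group and prior VR; and post-test score on group, baseline score and prior VR. Fix the coding of prior VR before data are seen.
3. Report the adjusted group difference and the prior-VR coefficient with 95% CIs. Report the group-by-prior-VR interaction as a secondary estimate, described as imprecise.
4. Name the primary model in advance and state its assumption. The change-score model assumes parallel trends given prior VR. The baseline-adjusted model assumes that students alike in baseline and prior VR would have equal expected post-test scores without VR training. Say plainly when the two disagree.
5. State that adjustment cannot remove unmeasured differences with one intact group per arm.

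The cost is plan wording and a few regressions per outcome; every variable is already to be collected. The downsides are a little more analysis work, a linear model applied to summed Likert scores (partly covered by robust standard errors and the retained rank test), more results per outcome, and two models that may disagree.

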### **Ethical consolidation**

This study will follow the Hong Kong Polytechnic University ethics procedure and ethical clearance will be applied. All data collected will be stored in a secured area. The researcher will also reassure the participants of the right to withdraw from the study at any time. The video recorded for review will be destroyed after data analysis.

## Conclusion

Non-technical skills in the healthcare industry are vital to maintaining patient safety and preventing errors. The effectiveness of the technology-assisted teaching pedagogy is well studied. However, the use of VR to develop students' non-technical skills in healthcare education field is not common. The proposed study investigates the effectiveness of the VR training system on situation awareness, communication skills and self-confidence in learning development in university nursing students.

